## 5.0 INTERPRETATION OF EXPECTED RESULTS

For each CSE performed, multiple factors will be recorded: patient's age, height, weight, time to onset of T10 sensory level, peak sensory level and peak level of motor block (described by modified Bromage scale), patient pain during surgery, need to use epidural catheter, time to return of motor function, and length of PACU stay. Data will be analyzed by our statistician looking for significant differences in outcomes in the BE group compared to the B group.

## 6.0 ELIGIBILITY & EXCLUSION CRITERIA

### **Eligibility criteria:**

1. Any patient 18 or older undergoing D&C or cerclage placement under neuraxial anesthesia.

### **Exclusion criteria:**

1. BMI >35

2. Coagulopathy
3. Platelets < 80,0000
4. Prior spinal surgery
5. Intracranial or spinal mass
5. Allergy to study medications
6. History of lower extremity weakness

## 7.0 RANDOMIZATION/RECRUITMENT PROCEDURES

**Recruitment:** Eligible patients will be identified using the Horizon WIC operating schedule. Once identified, one of the study investigators will screen the patients using the inclusion and exclusion criteria. If patient has no contraindications, the study will be explained and risks and potential benefits will be discussed by one of the study investigators.

**Randomization:** Once the patient is enrolled into the study, they will randomly be assigned into one of the two study groups. Randomization will be performed via random drawing of sealed envelopes which indicate either B or BE. A qualified anesthesia provider independent of the study will perform the spinal procedure and administer the medication in routine fashion.

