### 3. SIGNIFICANCE OF STUDY

Neuraxial anesthesia remains the standard of care for parturients or recently postpartum patients requiring anesthesia for surgical procedures. At UAB, we routinely use 10-12mg of hyperbaric bupivacaine with 12.5mcg of fentanyl in our spinal anesthetics for these procedures. This combination effectively delivers fast and reliable analgesia for our patients, but also comes with the burden of prolonged sensory/motor blockade and ultimately an extended stay in PACU(>1 hour). Many of these patients are otherwise stable but must be maintained under our care until their motor block recedes. More time spent in the PACU equates to an increase in healthcare resource and cost consumption, much of which we do not recuperate. If we are able to demonstrate satisfactory surgical anesthesia with an agent that could provide a faster recovery and shorter PACU stay, we could decrease our cost of care for these cases. Another important factor that must be considered is patient satisfaction. It is thought that patients just recently having a D&C for fetal demise suffer emotional distress as they sit in PACU and hear all of the new mothers interact with their children for the first time. Decreasing the length of time in the PACU will decrease healthcare resource and cost consumption and potentially lessen some of the emotional hardships suffered by our patients.

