#### **11.0 STATISTICAL CONSIDERATIONS**

**Demographic Variables:** Age, weight, height, past medical history, procedure type.

**Control Variables:** Group B (10 mg of preservative-free isobaric bupivacaine and 12.5 mcg of fentanyl) vs Group BE (5 mg of preservative-free isobaric bupivacaine and 12.5 mcg of fentanyl with 10 ml of sterile saline through epidural)

**Study Variables:** The primary endpoint is the time until PACU discharge requirements are met. The secondary endpoints are time elapsed to achieve T10 sensory level, degree of peak motor blockade, time elapsed until motor block regresses to modified Bromage score < 2, duration of the spinal block, and patient satisfaction score.

**General Data Analysis:** All demographic and clinical variables with continuous measures will be expressed as means and standard deviations; categorical factors will be expressed as proportions. For non-normal data, the medians and interquartile ranges will be displayed. The distribution of the continuous factors will be examined using the Kolmogorov-Smirnov test. For data that are normally distributed, One-way analysis of variance (ANOVA) will be used to compare the two types of anesthesia. For data that are not normally distributed, the Kruskal-Wallis test will be used for comparisons. Chi-square and Fisher's exact tests will be used to analyze categorical data. For all comparisons, a p-value less than 0.05 will be considered statistically significant.

**Primary Outcome Analysis.** The primary endpoint for this study is the length of time until PACU discharge requirements are met. One-way ANOVA (or the Kruskal-Wallis test, as appropriate) will be used to assess whether PACU length of stay is significantly associated with type of spinal anesthesia. Linear regression will also be used to evaluate the relationship between method of spinal anesthesia and PACU length of stay, while controlling for relevant clinical and demographic variables.

**Secondary Outcome Analysis:** One-way ANOVA will also be used to compare groups on time to achieve T10 sensory level, degree of peak motor blockade, time elapsed until motor block regresses, and patient satisfaction.

**Additional Data Analysis:** N/A

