**Statistical Power and Sample Size Estimates:** Approximately 40 subjects (20 per group) are expected to be enrolled in this study. Assuming a standard deviation of 20 minutes for PACU length of stay, a study with this sample size will have approximately 80.7% power to detect a 20 minute difference and approximately 98.9% power to detect a 30 minute difference in PACU length of stay between Group B and Group BE.

**Study Population Availability:** Approximately 3-5 of these procedures are performed per week, which equals about 200 cases per year. About 80% of these cases will be done under spinal anesthesia for a total of 160 per year. Assuming a 50% enrollment rate, it should take 7 to 8 months to complete enrollment.

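### Procedure type (cerclage or D&C) is neither a randomization stratum nor a named covariate, so chance differences in case mix add avoidable noise at 20 per arm

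*Combined protocol and SAP*

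**What the plan says.** Section 7.0 describes allocation in one sentence: "Randomization will be performed via random drawing of sealed envelopes which indicate either B or BE". No stratum, block or minimisation appears there or elsewhere. Section 6.0 admits both procedures: "Any patient 18 or older undergoing D&C or cerclage placement under neuraxial anesthesia". Patients are identified from the operating schedule, so the procedure is known before the envelope is drawn. The expected split between procedures is not given.

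Section 11.0 lists the demographic variables as "Age, weight, height, past medical history, procedure type". The primary comparison of PACU time is one-way ANOVA or Kruskal-Wallis. A linear regression is added that controls for relevant clinical and demographic variables, without naming them. For the secondary outcomes, "One-way ANOVA will also be used to compare groups on time to achieve T10 sensory level", and the same sentence covers peak motor block, motor regression and satisfaction. No covariate is mentioned for any of these.

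On size: "Approximately 40 subjects (20 per group) are expected to be enrolled in this study".

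**The concern.** Two different operations share one small randomization. Where an outcome depends on the operation, a chance excess of one procedure in one arm moves the observed treatment difference, and no analysis is committed to removing that movement.

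The protocol's own definitions make this plausible for some outcomes:

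- **PACU time.** In Section 1.0 the primary clock starts at PACU admission, while block duration runs from placement. Operating time therefore uses up block time before the primary clock starts. If the operations differ in length, PACU time would differ in the opposite direction.
- **Block quality.** This is judged by intraoperative pain and epidural supplementation, both of which can depend on the surgery.
- **Satisfaction.** Section 3 says it is thought that "patients just recently having a D&C for fetal demise suffer emotional distress as they sit in PACU", and Section 8.0 has all endpoints measured before PACU discharge.

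At stake is the reading of a single 40-patient result that may carry an uneven case mix.

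**Working it through.** **Inputs from the plan.** 20 per arm, two-sided alpha 0.05 (the sidedness is assumed), target difference 20 minutes, and "Assuming a standard deviation of 20 minutes for PACU length of stay".

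**Assumed, because the plan gives no figure.** Share of the rarer procedure 20% to 50%; difference in mean PACU time between procedures (the gap G) 0, 10 or 20 minutes.

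**The plan's own power.** Section 11.0 states "approximately 80.7% power to detect a 20 minute difference and approximately 98.9% power to detect a 30 minute difference". An exact t calculation with 20 per group and SD 20 gives 86.9% and 99.6%. The stated pair matches 17 per group (80.7% and 98.9%). The plan states no loss rate that would explain this. It is a separate matter and errs towards understating power. The baseline below is 87%.

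**Step 1: how often the mix differs.** Let K of the 40 patients have the rarer procedure and X of them fall in one arm of 20. X is hypergeometric and the arms differ by |2X − K| patients.

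| Share (K) | 4 or more (20 points) | 6 or more (30 points) |
|---|---|---|
| 20% (8) | 24% | 4% |
| 30% (12) | 30% | 8% |
| 40% (16) | 33% | 10% |
| 50% (20) | 34% | 11% |

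The SD of the difference in share is √(p(1−p)·4/39), which is 13 points at p = 0.2 and 16 points at p = 0.5. Section 7.0 does not say that the envelopes fix the arms at 20 each. If arm sizes are left to chance, a gap of 20 points or more occurs in 13% to 22% of trials; the SD of the difference is unchanged. A split of 25:15 or worse then occurs in 15%.

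**Step 2: what an imbalance does to PACU time.** Shift = (imbalance / 20) × G.

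- 4 patients: 4/20 × 10 = 2 minutes, or 4/20 × 20 = 4 minutes.
- 6 patients: 6/20 × 10 = 3 minutes, or 6/20 × 20 = 6 minutes.

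With a 50:50 mix, an unfavourable 4-patient imbalance leaves the unadjusted test with about 80% power (G = 10) or 72% (G = 20) for a 20-minute effect. A favourable one gives 93% or 98%. With no treatment effect, the chance of a significant result given a 6-patient imbalance is 6.0% (G = 10) or 10.7% (G = 20).

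**Step 3: averaged over all draws.** Simulation with 20,000 runs per cell, 50:50 mix, total SD held at 20 minutes. Power for 20 minutes:

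| G (min) | Unstratified, unadjusted | Unstratified, adjusted | Balanced within procedure, adjusted |
|---|---|---|---|
| 0 | 86.8% | 85.8% | 86.9% |
| 10 | 86.8% | 87.8% | 88.9% |
| 20 | 86.6% | 93.9% | 94.2% |

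Simulation error is about √(0.87 × 0.13 / 20,000) = 0.2 points. Type I error of the unstratified, unadjusted test is 5.1% to 5.3%. Balancing within procedure but leaving procedure out of the test makes it conservative: 4.3% at G = 10 and 2.2% at G = 20.

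**The case against.** The strongest reply is that nothing here is invalid. Simple randomization is unbiased, the unadjusted test holds close to 5% over all draws, and its standard error already reflects chance imbalance. That stands: the loss is in precision and in how far a single result can be trusted, not in validity.

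A reader might infer that an uneven mix shifts every unadjusted comparison. The documents do not support that. They give no reason why the operation should change time to T10 or peak motor block, which describe onset of the injected block. For satisfaction the support is thin: Section 3 reports a belief about distress with no size attached, and Section 8.0 records satisfaction with the anesthetic, not with the PACU stay.

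A reader might also infer that the secondary comparisons could not be repaired later. They could, because procedure type is recorded. The weakness is that the adjustment is not prespecified.

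The procedure gap itself is assumed. Section 8.0 gives one figure, about 1 hour in PACU, for all patients. A 20-minute gap is as large as the target effect and the planning SD, so it is an upper illustration. At 10 minutes the typical consequences are small.

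Finally, the planned regression can include procedure type. That also stands, but it sits beside an unadjusted primary test, leaves the covariates to later choice, and does not extend to the secondary outcomes.

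**Conclusion.** The point holds as one of efficiency and prespecification. Allocation ignores a known baseline factor, and no analysis commits to it. A 20-point difference in case mix would arise in about a quarter to a third of draws with fixed 20:20 arms. The consequence is a shift of 2 to 4 minutes in PACU time for a 4-patient imbalance, if the procedures differ by 10 to 20 minutes. Imbalances of 6 or more patients are uncommon.

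The outcomes plausibly exposed are PACU time, block quality and satisfaction. A claim of systematic bias, or of an effect on all endpoints, would go beyond the documents. All sizes rest on the assumed mix and gap; if procedure has no effect on an outcome, imbalance does it no harm. Adjustment brings most of the benefit when the gap is large. Stratification adds 1.1 points at a 10-minute gap (88.9 − 87.8) and 0.3 at 20 minutes (94.2 − 93.9).

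**What to change.** **Section 11.0 (main change).** Name procedure type as a covariate in the PACU-time regression and make that model the primary comparison, with the unadjusted test as a supporting analysis. Include procedure type in the secondary outcome models as well. Where Kruskal-Wallis would have been used, specify a rank test stratified by procedure.

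**Section 7.0 (cheap addition).** Prepare two envelope series, one for cerclage and one for D&C, in permuted blocks of randomly varying size such as 4 and 6, generated by someone who does not recruit. Open the next envelope in the patient's own series. Always keep procedure in the model when stratifying, since leaving it out makes the test conservative.

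**Cost.** No extra patients or data. Adjustment uses one degree of freedom and costs about 1 point of power if procedure has no effect (86.8% to 85.8%); with balance within procedure that loss disappears (86.9%). With blocks of up to 6, each series can end at most 3 patients apart, so the final split could be as uneven as 23:17. The change to the envelopes must be made before enrolment, and the change to the analysis before any outcome data are examined.

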## 8.0 STUDY INTERVENTIONS/PROCEDURES

### 1. **Study design.**

There will be two groups in this study differentiated by the dose of LA: 10 mg of preservative-free isobaric bupivacaine with 12.5mcg of fentanyl (B) and 5 mg of preservative-free isobaric bupivacaine with 12.5mcg of fentanyl (BE). Patients undergoing cerclage placement or D&C who meet the inclusion/exclusion criteria will be approached about the study. Informed consent will be obtained, and the patient will be randomized into either the B or BE group. The CSE will be performed by a certified anesthesia provider at UAB in the standard fashion. Patients in the B group will have an epidural catheter placed after the spinal. Patients in the BE group will receive a 10 mL bolus of sterile saline through the epidural needle before the epidural catheter is placed. Routine care will be provided to the patient throughout the procedure by an anesthesia provider that is independent of the study. This includes administering LA through the epidural catheter to ensure patient comfort during the surgery. Data pertinent to the study will be recorded on the IRB-approved data sheet that will be kept locked in a secure cabinet in the PI's office. Information recorded will include: time of spinal placement, presence of epidural saline bolus, drugs administered, time to achieve T10 sensory level to pinprick, peak sensory and motor block, PACU times, and patient satisfaction with her anesthetic. Information from the data sheet will be

transferred to a secured password protected database. Once a sufficient number of participants have been recruited, our data will be assessed by a statistician.

2. **Comparison groups.**

(B) Preservative-free isobaric bupivacaine 10 mg with 12.5mcg of fentanyl  
 (BE) Preservative-free isobaric bupivacaine 5 mg with 12.5mcg of fentanyl with addition of 10 mL of sterile saline for EVE

3. **Study and timeline of interventions.**

Discussion of the study to potential participants and obtaining informed consent will take about 15 minutes. As patients will receive routine care, no added time will be needed to perform this study. Therefore, routine CSE placement will take about 15 minutes, the operative procedure about 1 hour, and PACU recovery about 1 hour. Total time for recruitment and completion of the study will take approximately 2 hours and 30 minutes per patient, with 2 hours and 15 minutes being routine care. Total recruitment will take approximately one year to complete.

4. **Measured end-points and timeline of end-point measurements.**

All endpoints will be measured prior to discharge from the WPACU

- a. Time until WPACU discharge criteria met
- b. Time elapsed until T10 sensory level achieved
- c. Time until score of <2 reached on Modified Bromage scale
- d. Duration of the spinal block
- e. Patient satisfaction of a scale of 1-10
- f. Patient pain during surgery
- g. Need to use epidural during surgery

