Once informed consent is obtained, study participants will be randomized into two different groups: low dose spinal bupivacaine with EVE (BE), and standard-dose spinal bupivacaine (B). Spinal anesthesia will be administered via CSE in routine fashion by a qualified anesthesia provider that is independent of this study. The primary outcome will be total PACU time defined as the time from admission to PACU until the time patient meets PACU discharge criteria (Modified Bromage scale of < 2, blood pressure and heart rate within 20% of baseline, return of baseline oxygenation status as measured by pulse oximetry, alert with baseline mentation, pain well controlled) (Modified Bromage scale: 0-ability to maintain leg lift for prolonged period; 1- ability to lift legs briefly; 2- ability to bend knees; 3- ability to wiggle toes; 4- no movement of lower extremities). Secondary outcomes will be: (1) time until sensory level of T10 achieved, (2) degree of peak motor block after spinal placement (3) time until return of motor function (Modified Bromage score < 2), (4) duration of the block (defined as time from placement until PACU discharge criteria met), (5) quality of the block (as determined by any pain reported during surgery and/or the need to supplement through the epidural) and (6) patient satisfaction (based off of a 0-10 scale). A total of 40 patients will be recruited for the study.

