### 4.0 OBJECTIVE(S) & HYPOTHESIS

**Purpose:** The purpose of this study is to conduct a single site, prospective, randomized study to compare low-dose bupivacaine with fentanyl in combination with EVE to our traditional bupivacaine dose with fentanyl for short obstetric procedures.

**Outline of Therapy:** Patients who are undergoing either placement of cerclage or D&C will be randomized into two groups: 2 ml of preservative-free, isobaric bupivacaine 0.5% (10mg) with 12.5mcg of fentanyl (Group B), or 1 ml of preservative-free isobaric Bupivacaine 0.5% (5mg) with 12.5mcg of fentanyl (Group BE). Group B will serve as our control group. Each group will receive the spinal medications via a CSE technique. The epidural catheter will then be inserted into the epidural space in the B group, whereas a 10 mL bolus of sterile

saline will be injected through the epidural needle into the epidural space before the epidural catheter is threaded in the BE group. All CSEs will be placed by certified anesthesia providers working at UAB's WIC. Also, the epidural catheters that are placed in both groups can be used at any time throughout the procedure if the surgical anesthesia level is believed to be inadequate. Standard demographic data (age, height, and weight) will be collected in addition to data pertaining to primary and secondary endpoints.

**Primary endpoints or outcomes:** The primary outcome will be time until PACU discharge requirements are met (modified bromage scale of < 2, blood pressure and heart rate within 20% of baseline, return of baseline oxygenation status, alert with baseline mentation, pain well controlled).

**Secondary endpoints or outcomes:** Secondary outcomes will be the time elapsed to achieve T10 sensory level to pinprick, degree of peak motor blockade (recorded at the time of consecutive identical dermatomal sensory levels), time elapsed until motor block regresses to modified Bromage score < 2, duration of the block, quality of the block (as determined by any pain reported during surgery and/or the need to supplement through the epidural), and patient satisfaction.

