**Study Hypothesis:** We hypothesize that patients in the EVE group will meet the criteria for PACU discharge significantly quicker than the traditional bupivacaine group while having adequate surgical anesthesia. We also hypothesize that patients in group BE will reach a T10 sensory level quicker, have a lesser degree of peak motor blockade, and will have a faster recovery of motor function.

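### Cheap improvement: set one PACU checking interval for both arms, separate the readiness record from the allocation entries, and replace the free envelope draw with numbered envelopes

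*Combined protocol and SAP*

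**What the plan says.** Section 1.0 defines the primary outcome as "the time from admission to PACU until the time patient meets PACU discharge criteria", and Section 4.0 repeats it with the same criteria. They are a motor-block score, blood pressure and heart rate, oxygenation, mentation and pain control. Section 8.0, item 4, gives the timing of all endpoints in one line: "All endpoints will be measured prior to discharge from the WPACU".

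Staff independence is stated for the person who places the block (Section 7.0) and for care during the operation (Section 8.0, item 1): "Routine care will be provided to the patient throughout the procedure by an anesthesia provider that is independent of the study". Nothing comparable is said about PACU. Section 8.0, item 1, also lists the saline bolus, the drugs given and the PACU times among the entries on one data sheet.

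On allocation, Section 7.0 says: "Randomization will be performed via random drawing of sealed envelopes which indicate either B or BE". The draw follows enrolment. The text does not mention numbering, opacity, a generated list or a custodian.

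**The concern.** Readiness has to be observed. Section 3 says that many of these patients are otherwise stable but "must be maintained under our care until their motor block recedes". It is an inference, though a natural one, that the recorded time is then partly the time at which someone looked. The stated hypothesis has a direction: "patients in the EVE group will meet the criteria for PACU discharge significantly quicker than the traditional bupivacaine group". If one arm were checked sooner than the other, the gap would enter the primary endpoint minute for minute and look like a treatment effect. Such a gap would be tied to the arm itself, so the covariate regression in Section 11.0 could not remove it.

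Keeping allocation entries and PACU times on one sheet could show the group to whoever records readiness. A lesser matter is the free draw: if an envelope were put back or set aside, the record might not show it.

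**Working it through.** **Inputs.** Section 11.0 gives 20 per group, SD 20 minutes, significance at 0.05, and one-way ANOVA as the first-named primary test (with two groups, the same as a t-test). Sidedness is not stated; two-sided is assumed. Every bias size and checking interval below is an assumption, because the documents give none.

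**The plan's own figure.** With these inputs the noncentral t gives 86.9% power for 20 minutes and 99.6% for 30 minutes. The plan states 80.7% and 98.9%, which match 17 per group exactly. The stated power is thus lower than its inputs imply, and an unstated allowance such as 15% loss (17/0.85 = 20) would explain it. This does not affect the present point, which uses only error rates and changes in power.

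**Step 1: a systematic timing difference with no true effect.** The standard error of the difference is 20 × √(2/20) = 6.32 minutes. The noncentrality is shift/6.32, on 38 degrees of freedom.

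| Assumed shift (min) | Noncentrality | False-positive rate |
|---|---|---|
| 0 | 0 | 5.0% |
| 1 | 0.16 | 5.3% |
| 2 | 0.32 | 6.1% |
| 5 | 0.79 | 12.0% |
| 10 | 1.58 | 33.8% |

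**Step 2: how unequal checking could produce a shift.** If readiness is recorded at the next scheduled check, the mean delay is about half the interval. Simulation with both arms truly equal (mean 60, SD 20, 200,000 trials) gives:
- 15 minutes in one arm and 5 in the other: 7.5 − 2.5 = 5 minutes, 11.9%, whichever arm is checked more often.
- 15 and 10: 7.5 − 5 = 2.5 minutes, 6.7%.
- 15 in both: 0 minutes, 5.0%.

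**Step 3: envelope exchanges.** Suppose half the patients recover 20 minutes slower than the other half, with total SD 20. Exchanging one slow BE patient for one fast B patient lowers the BE mean by 20/20 = 1 minute and raises the B mean by 1 minute, a 2-minute shift. One, two or three exchanges shift the difference by 2, 4 or 6 minutes. The unadjusted test then rejects in about 6%, 10% and 16% of simulated trials. With a 10-minute gap the rates are 5.3%, 6.2% and 7.5%. If the slow/fast factor is recorded and entered in the Section 11.0 regression, the 20-minute case returns to 5.1%, 5.0% and 5.0%.

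**Step 4: precision under interval checking.** A common interval k inflates the SD to √(400 + k²/12). Power for a 20-minute difference falls from 86.9% to 86.7%, 86.2% or 85.4% at k = 5, 10 or 15, a loss of about 0.2, 0.7 or 1.5 points. The comparison is with exact timing.

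**The case against.** The strongest reply is that no documented mechanism makes the arms differ. A reader might infer from the silence that they are checked differently, or that the readiness judge knows the group and acts on it. The documents support neither. Section 8.0, item 3, counts 2 hours 15 minutes as routine care, which is the sum of its 15-minute CSE, 1-hour operation and 1-hour PACU recovery. PACU is therefore routine care in both arms. Most discharge criteria have explicit thresholds, leaving limited room for judgement, although mentation and pain control are softer. The data sheet may already fix an interval or name a recorder. All of this stands, and it limits the point to prevention.

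The reply on envelopes also stands in part. The draw follows enrolment, an independent provider places the block, and the planned regression can recover the error rate for a recorded prognostic factor. It does not cover unrecorded factors or the unadjusted ANOVA or Kruskal-Wallis test, which the plan names ahead of the regression.

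Masking will be imperfect. In its favour, "Each group will receive the spinal medications via a CSE technique", and "the epidural catheters that are placed in both groups can be used at any time throughout the procedure", so the technique alone does not reveal the group in PACU. Against it, motor block is scored directly and is expected to be less in BE, and the anesthesia record may have to be consulted.

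**Conclusion.** The gap in the protocol text is real: no common interval, no masking of readiness judge or patient, allocation entries and PACU times on one sheet, and an unordered draw. It warrants a cheap safeguard. It is not evidence of a biased trial.

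The error rates show sensitivity and do not estimate this trial's error. A systematic difference of 1 to 2 minutes would matter little (5.3% to 6.1%); about 5 minutes or more would matter with 20 per group (12.0% or higher). Equal intervals in both arms keep the rate at 5%. The envelope figures of about 6%, 10% and 16% apply to the unadjusted test under an assumed 20-minute prognostic gap, with recovery class known beforehand and envelopes deliberately exchanged. They should not be read as surviving adjustment for a recorded factor.

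Nor should the power losses in Step 4 be read as the price of the change. The current plan does not promise exact timing either, and unscheduled checks also lose precision.

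**What to change.** 1. **Section 7.0.** Replace the free draw with sequentially numbered opaque envelopes, prepared from a computer-generated list by someone who does not enrol patients, and opened in order after consent. Blocking with concealed block sizes and stratification by procedure are optional.
2. **Section 8.0, readiness record.** The person who already judges PACU readiness records the time on a separate page without dose, saline or top-up entries. Where care allows, neither that person nor the patient is told the group. If the readiness judge also gave the anesthetic, keep the common interval and patient masking only.
3. **Section 8.0, interval.** State one checking interval in advance, the same for both arms. If the data sheet already has one, copy it into the protocol.

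The cost is a sentence on the interval, one data-sheet page, one list and a set of numbered envelopes. No assessor is added and N stays at 40. The downsides are slight administrative work and masking that may be only partial.

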### **Side Effects:**

Adverse effects indicated in *italics* are the most frequent adverse effects.

Adverse events in **bold** are severe/life-threatening, otherwise they are mild to moderate in reaction.

- CNS: Tinnitus, perioral numbness, seizure, coma
- CV: Hypotension, arrhythmia, bradycardia, heart block, cardiac arrest
- EENT: N/A
- ENDO: N/A
- GI: Fecal Incontinence
- GU: Urinary incontinence
- INTEG: N/A
- MS: N/A

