#### **Side Effects:**

Adverse effects indicated in *italics* are the most frequent adverse effects.

Adverse events in **bold** are severe/life-threatening, otherwise they are mild to moderate in reaction.

- CNS: Confusion, loss of consciousness, headache
- CV: Hypotension
- PULM: Respiratory depression, Apnea
- EENT: N/A
- ENDO: N/A
- GI: Constipation, Nausea
- GU: Urinary retention
- INTEG: N/A
- MS: N/A

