## 13.0 REPORTING ADVERSE EVENTS

Adverse events will be reported to the IRB.

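### None of the named drug risks is a listed data item, endpoint or analysis variable, and endpoint measurement stops at PACU discharge, so the plan gives no by-arm safety comparison

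*Combined protocol and SAP*

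**What the plan says.** The timing rule is in Section 8.0 item 4: "All endpoints will be measured prior to discharge from the WPACU". No later contact or chart review is described.

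There are two lists of what is recorded. Section 8.0 item 1 begins "Information recorded will include: time of spinal placement, presence of epidural saline bolus, drugs administered, time to achieve T10 sensory level to pinprick" and goes on to peak block, PACU times and satisfaction. Section 5.0 adds "patient pain during surgery, need to use epidural catheter, time to return of motor function, and length of PACU stay". Neither list contains an adverse event, a blood pressure, a heart rate or an oxygen saturation.

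The endpoints in Sections 1.0, 4.0 and 8.0 item 4 cover time to discharge criteria, block onset, motor block and recovery, duration, quality of the block (pain and epidural supplementation) and satisfaction. Section 11.0 follows them ("The secondary endpoints are time elapsed to achieve T10 sensory level, degree of peak motor blockade" and so on) and names no safety variable.

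Section 10.0 names the risks. The bupivacaine entry has "CV: Hypotension, arrhythmia, bradycardia, heart block, cardiac arrest" and also urinary and fecal incontinence. The fentanyl entry has "PULM: Respiratory depression, Apnea" and "GU: Urinary retention", as well as nausea, headache and constipation.

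The whole of the adverse-event plan is Section 13.0: "Adverse events will be reported to the IRB". It gives no definition, collection form, time window or summary by arm.

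**The concern.** The claimed benefit is that patients become ready to leave sooner. To weigh that, a reader needs to know what happened to the same patients in the way of hypotension, bradycardia, desaturation and nausea, and whether problems appeared after they left. A report to the IRB does not put those events into the trial dataset, and events that were not collected in a defined way cannot be reliably compared later.

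The lower dose does not settle the question by argument, because BE changes two things at once: 5 mg instead of 10 mg of bupivacaine, and 10 mL of epidural saline. Section 2 cites work in which epidural saline moved contrast up by as many as four levels, and a study of 10 mg with volume extension in which the block reached T2, while only T10 is needed here. Peak sensory level is to be recorded. The blood pressure and heart rate that might accompany a high block are not.

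A second problem arises if events are counted afterwards up to discharge. The end of that period is tied to the primary outcome, so the two arms may be observed for different lengths of time.

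**Working it through.** **Step 1. Where each named risk appears.**

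| Risk (Section 10.0) | Data lists (5.0; 8.0 item 1) | Endpoints (1.0; 4.0; 8.0 item 4) | Section 11.0 |
|---|---|---|---|
| Hypotension, bradycardia, arrhythmia | No | No; blood pressure and heart rate only as discharge criteria | No |
| Respiratory depression, apnea | No | No; oxygenation only as a discharge criterion | No |
| Nausea, headache, constipation | No | No | No |
| Urinary retention, urinary or fecal incontinence | No | No | No |

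The one indirect trace is the listing of drugs administered, which could show that an event was treated. Vital signs enter the primary outcome only through the time at which all the criteria are met. An intraoperative event that resolves before then need leave no mark in the listed data.

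**Step 2. Length of observation.** Section 8.0 item 3 gives about 15 minutes for the CSE, 1 hour for the procedure and 1 hour in PACU: 15 + 60 + 60 = 135 minutes. This reproduces its own figure of 2 hours 15 minutes of routine care. Section 11.0 powers the trial for differences of 20 and 30 minutes in PACU stay. Taking 135 minutes as Group B's total:

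- 20/135 = 14.8%
- 30/135 = 22.2%

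On the plan's own figures, BE would be observed for 15% to 22% less time from the start of placement. As a share of a 60-minute PACU stay the gap is 20/60 = 33% to 30/60 = 50%, but much of the exposure of interest comes before PACU. With no treatment effect the gap is zero.

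Only the two differences are taken from the power statement. Its power values do not affect this point.

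**Step 3. What a by-arm table could show at 20 per arm.** With zero events in n patients, the exact one-sided 95% upper limit solves (1 − p)^n = 0.05, so p = 1 − 0.05^(1/n). For n = 20, p = 1 − 0.05^(1/20) = 13.9%.

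Power of Fisher's exact test at two-sided 0.05, by enumeration, under assumed event rates that are not in the documents:

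| Assumed rates | Power |
|---|---|
| 40% v 20% | 19% |
| 50% v 25% | 27% |
| 50% v 10% | 74% |

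Halving a common event would usually be missed. The table can describe, but it cannot test safety.

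**The case against.** Several points on the other side are sound and limit what can be said.

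- **A reader might infer that BE is observed for less time by design.** The documents do not support that. Both arms have the same stopping rule, discharge. A shorter period in BE is the hypothesis.
- **A reader might infer that any count up to discharge would favour BE.** That is too strong. Events during placement and surgery precede PACU in both arms. The discharge criteria require acceptable blood pressure, heart rate, oxygenation, mentation and pain control, so a patient with one of these problems unresolved is observed for longer. The documents give no event rate and plan no such count, so no spurious risk ratio is offered here.
- **A reader might infer that nothing is captured after discharge.** The timing rule covers endpoints. Section 13.0 sets no time limit on reporting to the IRB.
- **The data sheet itself is not in the documents.** The list in Section 8.0 item 1 is open-ended and demonstrably incomplete: it omits intraoperative pain, which Section 5.0 includes. An adverse-event field cannot be ruled out. Even if one exists, Section 11.0 names no variable from it. Its general provision for chi-square and Fisher tests does not say what would be compared.
- **Fentanyl is 12.5 mcg in both arms.** Respiratory depression, nausea, urinary retention and headache are listed only under fentanyl, so the dose contrast bears most directly on hypotension and bradycardia. The harm of a lower dose that the protocol itself discusses, an inadequate block, is measured through pain and epidural use.

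These points narrow the claim about unequal observation. They do not supply a comparison by arm.

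**Conclusion.** The concern holds in a limited form. No named drug risk is a listed data item, endpoint or analysis variable, endpoint measurement ends at PACU discharge, and the only adverse-event provision is reporting to the IRB. The trial as written could therefore conclude that BE recovers faster while having nothing comparative to say about harm. This should be corrected before enrollment.

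Unequal observation is a secondary and conditional matter. It amounts to 15% to 22% of the care period if the true difference is 20 to 30 minutes. It assumes that the 135-minute estimate describes Group B and that actual discharge follows closely once the criteria are met. Section 3 puts the usual PACU stay above 1 hour, which would make the share smaller.

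The gain from fixing this is descriptive. Twenty patients per arm cannot support a claim of equal or better safety.

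**What to change.** 1. Add to the data sheet and to Section 11.0, by arm: hypotension and bradycardia relative to baseline (the plan's existing 20% limit can serve as the recording definition), vasopressor use, oxygen desaturation and nausea, all taken from the anesthesia and PACU records.
2. Count these over a window observed for every patient in both arms, for example spinal placement to PACU admission. Spinal time and PACU times are already on the recorded list. Give the length of this window by arm.
3. Report PACU events separately, with observation time. PACU records end at discharge, so they cannot fill a common window that runs beyond it.
4. Where later records exist, add one chart check at the same fixed time in both arms for urinary retention, headache, rescue analgesia and return or readmission. State how many patients had records to check.
5. Present counts with exact confidence intervals, labelled descriptive, with no formal safety claim.

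The cost is a few fields, one chart check per patient and one table, for 40 patients. Blood pressure, heart rate and oxygenation are already assessed for the discharge criteria. The main weakness is that post-discharge records may be incomplete, since the protocol does not say where patients go afterwards. Nothing here alters treatment or the discharge criteria.
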